- ABR ABR form, General Assessment and Registration form, is the application form that is required for submission to the accredited Ethics Committee (In Dutch, ABR = Algemene Beoordeling en Registratie) AE Adverse Event AR **Adverse Reaction** CA **Competent Authority** ССМО Central Committee on Research Involving Human Subjects; in Dutch: Centrale Commissie Mensgebonden Onderzoek **Curriculum Vitae** CV cSrO₂ **Cerebral Regional Oxygen Saturation** DSMB **Data Safety Monitoring Board** EU **European Union** EudraCT European drug regulatory affairs Clinical Trials **FTOE Functional Tissue Oxygen Extraction** FiO₂ Fraction of inspired oxygen GCP **Good Clinical Practice** IB **Investigator's Brochure** IC Informed Consent IMP **Investigational Medicinal Product** IMPD Investigational Medicinal Product Dossier METC Medical research ethics committee (MREC); in Dutch: medisch ethische toetsing commissie (METC) NICU **Neonatal Intensive Care Unit** NIRS Near Infra Red Spectroscopy **Nitrous Oxide** NO (S)AE (Serious) Adverse Event SPC Summary of Product Characteristics (in Dutch: officiële productinfomatie **IB1-tekst**) Saturation if Oxygen measured by pulse oximetry SpO2 The sponsor is the party that commissions the organisation or Sponsor performance of the research, for example a pharmaceutical company, academic hospital, scientific organisation or investigator. A party that provides funding for a study but does not commission it is not regarded as the
 - sponsor, but referred to as a subsidising party.

SUSAR Suspected Unexpected Serious Adverse Reaction Vte Exhaled Tidal Volume Wbp Personal Data Protection Act (in Dutch: Wet Bescherming Persoonsgevens) WMO Medical Research Involving Human Subjects Act (in Dutch: Wet Medischwetenschappelijk Onderzoek met Mensen

SUMMARY

Rationale: Supplemental oxygen is given to preterm infants to ensure that they have an adequate arterial saturation (SpO₂). Fluctuations in the SpO₂ mean that the fraction of inspired oxygen (FiO₂) needs to be adjusted, a challenging and time consuming task. During the recovery of a desaturation there is often an overshoot, resulting in a period of hyperoxia. Hyperoxia interferes with vascular development of the lungs and eyes, and there is growing evidence that hyperoxia may be equally damaging to the developing brain.

An observational study conducted on our Neonatal Intensive Care Unit (NICU) has shown that infants on average spend only 54% of the time within the SpO_2 limits and 71 adjustments to the FiO₂ are made each day.

An automated controller (PRICO) has been developed that adjusts the FiO₂ based on the SpO₂. A study in a preterm lamb model has shown the effectiveness of this closed loop controller: less periods of desaturation and hyperoxia were demonstrated.

Objective: To test the safety and feasibility of a closed loop controller of the FiO_2 based on the measured SpO_2 in a NICU setting.

Study design: Neonates that are included will start with an 8 hour block of manual adjustment of the FiO₂. After completion of this block they will be switched to the automated control of the FiO2 for another 8 hours. After that they are switched back for another 8 hours of manual control, which is used to correct for any changes of the state of the neonate during the trial. For each ventilation type (high frequency , invasive and non-invasive) 24 patients will be included.

Study population: Neonates admitted to the NICU in the Erasmus MC, Rotterdam and Máxima Medical Centre, Veldhoven that are receiving respiratory support and a FiO_2 of more than 21%.

Intervention (if applicable): Automated control of the FiO₂ based on the measured SpO₂ during 8 hours.

Main study parameters/endpoints: The main parameter during the study is the time the SpO₂ spend within the target range. Secondary outcomes are the number of hyper and hypoxic events, average maximum and minimum SpO₂ during these events, number of FiO₂ adjustments (manual and automated) and cerebral oxygen saturation.

Nature and extent of the burden and risks associated with participation, benefit and group relatedness: There is no burden to the patient, and the risk is minimal. The same patient monitoring is used during the study as during routine care. The closed loop

algorithm is implemented in to the Acutronic Fabian HFO ventilator, so that no additional equipment is needed at the bedside.

The controller is designed so that it checks the input signals, the validity of the pulse oximetry and the quality of the ventilation. If any of the checked parameters is not within the specified limits the controller will not adjust the FiO_2 and give an alarm.

1. INTRODUCTION AND RATIONALE

Supplemental oxygen is given to preterm infants to ensure that they have an adequate arterial saturation (SpO₂), and is one of the most common therapeutic interventions in the neonatal intensive care unit (NICU) [1]. Fluctuations in the SpO₂ are dealt with by adjusting the fraction of inspired oxygen (FiO₂), a challenging and time consuming task. During the recovery of a desaturation there is often an overshoot, resulting in a period of hyperoxia. Both hypoxia and hyperoxia must be avoided because of their detrimental effects on morbidity and mortality in these children. While hypoxia may lead to direct and indirect cellular damage, hyperoxia has been associated with oxygen toxicity, oxidative stress [2], and chronic diseases of preterm infants such as bronchopulmonary dysplasia (BPD) [3] and retinopathy of prematurity (ROP) [4]. And there is growing evidence that hyperoxia may be equally damaging to the developing brain.

Large deviations from SpO₂ targets during routine NICU care of preterm infants have been observed in clinical observational studies, where SpO₂ target ranges are met during 50% of the time, and 71 adjustments to the FiO₂ are made each day. [5, 6]. Meeting SpO₂ targets affects morbidity and mortality, depending on the target range chosen [7-9]. Beside overall SpO₂ targets, variability of oxygenation influences outcome of preterm infants [4, 10, 11]. A promising solution to optimize oxygen therapy is the employment of an automatic "closed loop" system for regulation of FiO₂ based on SpO₂. Several clinical trials with different devices have proven feasibility of automated closed loop FiO₂ control in the NICU for various modes of ventilation, mixed populations, and by using different algorithms [5, 12-17]. In addition, an overall reduction of manual interventions during automated control was found in these studies, indicating facilitation of caretakers and nursing staff in clinical routine [18, 19]. However, at least one study raised concerns about safety, as time within target range was accompanied by an increase in time spent below saturation target range [16].

An automated controller (PRICO) has been developed by our research group that adjusts the FiO₂ based on the SpO₂. A study in a preterm lamb model has shown the effectiveness of this closed loop controller: less periods of desaturation and hyperoxia were demonstrated [20]. This new algorithm distinguishes itself from previous (published) algorithms by being faster, using a predictive model based on the trend of the SpO₂, and having a variable step size based on the current FiO₂. This study was specifically preformed in preterm lambs because of their similar physiology compared to preterm neonates. The transitional phase and incomplete development of the lungs are a key aspect to the fine tuning of the algorithm. This algorithm is tailored specifically to neonates. This patient group suffers more frequent changes in their saturation and require many adjustments of the oxygen therapy they receive. In addition their poor defence against oxygen free radicals means that they are more susceptible for too much oxygen, resulting in a very small target SpO₂ range. This range is different from almost all other patients because it targets a high saturation of only 95%. Because the high target is less than 100% is the actual reason that closed loop control based on SpO₂ is possible. Otherwise, when 100% SpO₂ is accepted, it is impossible to detect when too much oxygen is given. These lower SpO₂ targets also effect the actual uptake and transport of the oxygen, through the oxygen and the oxygen saturation, and is influenced by a number of factors. Fetal-haemoglobin, pH, temperature and CO₂ levels all effect the amount of oxygen that is actually transported by the blood at a certain saturation.

Besides this the actual lung volume compared to the circulated blood volume and cardiac output determine the timing of the closed loop controller. Combined with the narrow saturation target and the limited capacity of neonates it results in a very fast reacting but highly unstable system.

When a similar closed loop system would be developed for another patient group, both timing step size and gain would need to be tailored to their need. And a solution should be found when target saturation come close to or include 100% SpO₂ in order to detect and prevent overshoot.

We hypothesize that fully automated FiO_2 control conducted by this algorithm will keep SpO_2 within a predefined target range more time and with less deviation then during routine standard clinical care.

2. OBJECTIVES

Primary Objective: To test the safety and feasibility of a closed loop controller of the FiO_2 based on the measured SpO_2 in a NICU setting. This is determined by the time spend within the SpO_2 target range, and the number of times the SpO_2 was above and below the target.

Secondary Objective(s):

Track the usage of the fraction of inspired oxygen (FiO₂) during the periods. A higher oxygen use is only acceptable when it results in an improvement of the time spend within the oxygen saturation target range without a rise in hyperoxia. In all other cases a lower FiO_2 is preferred.

The respiratory support is analysed, to see if any changes were made to the ventilation settings. Changes to the pressure or timing can influence the need for additional oxygen.

Reduction in manual FiO_2 adjustments. Although the FiO_2 is adjusted automatically, it is still possible to adjust the FiO_2 by hand. This can be done on clinical indication. For example before an alteration to the respiratory support is made, before suctioning, or before respiratory support is halted for another reason.

[figure not shown]
When the infants are monitored with near infrared spectroscopy (NIRS) to monitor their cerebral oxygenation, this data will be analysed in order to see if automated oxygen control improves the stability of their cerebral oxygenation.

3. STUDY DESIGN

Neonates that are included will start with an 8 hour observational block to determine the baseline fluctuations during manual FiO₂ adjustment. After the first 8 hours they are switched to automated FiO₂ adjustment. During this time the FiO₂ is primarily controlled by the algorithm based on the measured SpO₂. Manual override is possible at all times, and logged. After the 8 hours of automated control (16 hours since the start) the neonate is switched back to manual control, and all parameters are again recorded for 8 hours. This second observational block is to make sure that the condition of the patient did not significantly change during the study period.

The care takers are not blinded to the intervention. During manual control FiO₂ is adjusted as it is during routine clinical care. During automated control the changes of the FiO₂ are clearly displayed on the screen of the Fabian HFO ventilator (Acutronic Medical GmbH, Hirzel, Switzerland), and the physicians are still able to adjust the FiO₂ manually (manual changes will be logged). The SpO₂ sensor (Masimo, Irvine, USA) for the adjustment of the FiO₂ is placed in addition to the routine pulse oximeter sensor (Masimo) that is connected to the patient monitoring system (Dräger M540, Lübeck, Germany). The routine pulse oximeter will provide the normal monitoring/alarming function.

The included patients are stratified based on the ventilation mode that they receive at the time of inclusion. This can be high frequency oscillatory ventilation (HFOV), mechanical ventilation with an endotracheal tube (intubated patients) or patients receiving non-invasive ventilation. Non-invasive ventilation consists of Continuous Positive Airway Pressure (CPAP) and can be given by a mask or bi-nasal prongs.

This stratification is done because the effectiveness of closed loop control is dependent on the efficiency of the ventilation. High frequency ventilation theoretically has the highest efficiency with the shortest transition times, followed by intubated patients receiving mechanical ventilation. Non-invasive ventilation is more dependent on the patient's own respiratory drive.

All modes use the flow sensor and ensure that ventilation occurs with adequate volume. Alarms are set to ensure that the clinical staff is warned when changes occur, and the PRICO algorithm is disabled when the alarm is triggered. Frequent apnea's can influence the results, but should be handled by the apnea back-up function. This function ensures adequate ventilation even during apnea's. Another variable during all ventilation modes is the amount of leak. Due to the un-cuffed tubes that are used in neonatology this is even the case in intubated patients. The amount of leak will be reported and analysed to ensure that there is no significant change between the different periods.

4. STUDY POPULATION

4.1 Population (base)

Patients admitted to the NICU and receiving ventilation and additional oxygen.

4.2 Inclusion criteria

In order to be eligible to participate in this study, a subject must meet all of the following criteria:

Neonates admitted to the NICU in the Erasmus MC, Rotterdam and Máxima Medical Centre, Veldhoven that are receiving respiratory support and a FiO_2 of more than 21% while having SpO₂ of 95% or less. No plans to change ventilation mode within the next 24 hours.

4.3 Exclusion criteria

A potential subject who meets any of the following criteria will be excluded from participation in this study:

Infants with any known congenital or chromosomal defects will be excluded from this study. When there is a plan to transfer the patient within 24 hours or change the ventilation mode within the next 24 hours the patient will not be included at that time.

4.4 Sample size calculation

The sample size calculation is based on the area under the curve for the SpO_2 . Giving a value that has a unit of [% SpO_2 *min]. A value of 30 can be reached by a SpO_2 of 30% outside of the target during 1 minute, or 30 minutes a SpO_2 that is 1% outside of the target. Values are normalized per hour.

During the animal trial conducted with this algorithm a reduction in the average of the area under the curve was found from 21 to 3 [%SpO₂*min per hour], with a standard deviation of 30 [%SpO₂*min per hour]. We accepted a significance level of 5% and a power of 80%. Because of the study design, each patient is its own control. Because of that only 22 patients are needed (Stata, StataCorp LP, USA). Because we want to show that the algorithm works in all 3 strata of ventilation we need three groups of 22 patients, and we expect a 10% dropout rate due to withdrawal or improvement in ventilation up to the point that additional oxygen is no longer needed, resulting in a total sample size of 72 patients.

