10.1 Primary study parameter(s)

The efficiency of the PRICO algorithm will be assessed by comparing the time spend outside and deviation from the SpO₂ target range. This is done with the area under the curve, normalized to a one hour period [SpO₂*min per hour]. It is calculated by taking the SpO₂ value from the patient monitor, logged once every second and, when it is outside the SpO₂ target range, subtract the target. The absolute value of all deviations is added together and divided by the length of all the recorded data in hours. The significance will be tested with a repeated measurement ANOVA.

The number of collected data points per period will be reported to show any possible bias due to unmeasurable SpO₂ levels, malfunctions or other events. This will be reported as a percentage of time recorded.

When there is a significant difference between the first and last period, the argument will be made that the patient changed overtime. In that case the automated period will be compared with the best of the two observational periods.

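### The 80% power in section 4.4 is per ventilation stratum; power to succeed in all three strata, the stated reason for three groups, is about 45-51%

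*Protocol*

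**What the plan says.** Protocol section 4.4 bases the sample size on the area outside the SpO₂ target range. In the lamb study "a reduction in the average of the area under the curve was found from 21 to 3" (in %SpO₂·min per hour), "with a standard deviation of 30". The operating characteristics are one sentence: "We accepted a significance level of 5% and a power of 80"%. The design is within-patient: "Because of the study design, each patient is its own control. Because of that only 22 patients are needed". The number is then tripled with an explicit reason: "Because we want to show that the algorithm works in all 3 strata of ventilation we need three groups of 22 patients". For losses, "we expect a 10% dropout rate due to withdrawal or improvement in ventilation", "resulting in a total sample size of 72 patients", which is 24 per stratum.

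Section 3 stratifies by ventilation mode at inclusion (HFOV, conventional ventilation through a tube, non-invasive). It does so because the controller's effectiveness is expected to depend on how efficient the ventilation is.

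For the primary parameter, section 10.1 says: "The significance will be tested with a repeated measurement ANOVA". Nothing in section 10 mentions ventilation mode or stratum, or what result would count as success in all three.

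**The concern.** The only power given is 80%, and it comes from a calculation for one group. The reason for having three groups is a conclusion about all of them together. Tripling a single-comparison sample size keeps the power of each comparison; it does not carry that power over to the requirement that all three succeed. A reader of 4.4 is not told how likely the trial is to reach the conclusion that justifies 72 rather than 24 infants.

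The analysis section does not close the gap. If 10.1 were carried out as one analysis over all infants, a significant result could come mainly from one or two modes. The protocol itself gives reasons to expect differences: section 3 ranks the modes by expected efficiency, section 6.2 says only intubated animals were tested, and section 6.3 says high frequency ventilation has not yet been tested clinically with such systems. At stake is whether the final statement about the three modes has a stated chance of being reached and a test that supports it.

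**Working it through.** **Inputs (section 4.4).** Difference δ = 21 − 3 = 18; SD = 30; significance 5%; power 80%; three strata; 22 evaluable per stratum; 72 enrolled; 10% dropout. Assumptions the protocol does not state: the test is two-sided, and 30 is the SD of the within-patient difference.

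**1. Reproduce the 22.** Paired comparison, normal approximation:

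n = [SD × (z₀.₉₇₅ + z₀.₈₀) / δ]² = [30 × (1.960 + 0.842) / 18]² = 21.8, so 22.

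A one-sided 5% test would give 17.2, so 18. Taking the test as two-sided and 30 as the SD of the difference gives the stated figure, and the 80% therefore describes one stratum.

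**2. Per-stratum power by the paired t-test.** Standardised effect 18/30 = 0.6, noncentral t, two-sided 5%:

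| Evaluable per stratum | Power, one stratum | Power, all three (cube) |
|---|---|---|
| 21 | 74.4% | 41.2% |
| 22 | 76.5% | 44.8% |
| 24 | 80.4% | 51.9% |

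So 24 evaluable infants are the smallest number reaching 80% in one stratum by this test. The protocol enrols 24 and expects 24 × 0.90 = 21.6 to remain.

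**3. Power for all three.** The strata contain different infants, so their results are independent and the powers multiply:

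- at the protocol's nominal power: 0.80³ = 0.512;
- by the paired t-test with 22 each: 0.765³ = 0.448.

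The range is therefore about 45% to 51%.

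**4. For scale.** A joint 80% needs 0.80^(1/3) = 92.8% in each stratum: 33 evaluable per stratum by the normal approximation, or 35 by the paired t-test. One pooled test on 3 × 22 = 66 infants would have 99.8% power. The chosen size therefore matches separate testing of each stratum at a nominal 80%. It is more than a pooled test needs and less than 80% power for all three would require.

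**5. Sensitivity.** The 51% follows from the protocol's own 80% whatever the SD. The t-based figure depends on the inputs:

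- If 30 were the SD within a period, the result would depend on the within-patient correlation, which the protocol does not give. By the normal approximation, joint power is 13% at correlation 0, 25% at 0.25, 52% at 0.5 and 94% at 0.75.
- If the two manual periods were averaged (assuming equal variances and equal correlations), the SD of the contrast falls to 30 × √0.75 = 26.0. Power is then 87% per stratum and 66% jointly.
- If the reduction were 22 instead of 18 (an illustrative value), joint power would be 74%.
- If one mode had a standardised effect of 0.4 (also illustrative) and the others 0.6, joint power would be about 25%.

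**The case against.** The strongest reply is that the protocol never promises 80% for the three strata together. It attaches 80% to a group of 22 and then asks for three such groups, and sizing each stratum separately is a recognised design. The primary objective in section 2 and the hypothesis in section 1 do not mention strata, and no joint success criterion is written down. This stands. A reader might infer that the protocol claims 80% for the all-strata conclusion, but the text does not say so. What remains is that 4.4 gives the all-strata aim as the reason for three groups and reports no power for it.

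A reader might also infer that 10.1 commits the trial to one pooled ANOVA. It does not: it names a method and is silent on pooling, and running that method within each stratum is a natural reading of sections 3 and 4.4. A SAP, which is not shown, may settle this. The point is therefore not that analysis detail is missing. It is that the aim in 4.4 and the test in 10.1 are not connected, and no SAP can make 22 per stratum deliver 80% for all three under the stated assumptions.

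Nor does the protocol plan to claim whichever stratum turns out significant, so inflated type I error cannot be charged against it. If all three must succeed, no adjustment is needed.

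Finally, the 45-51% is conditional. Section 6.2 describes separate automated and manual lamb groups, so 30 may not be a paired SD. Section 13.1 expects a larger effect than in animals, which would raise the power; the differences between modes expected in section 3 could lower it.

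**Conclusion.** The point holds in a limited form. The 22 is reproduced by the normal approximation, and 80% is a nominal per-stratum power (76.5% by the paired t-test). For the aim that justifies three groups, power is about 45-51%: even if the algorithm worked exactly as assumed in every mode, the trial would fail to show it in all three about half the time.

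This assumes independent strata, a difference of 18 in each, an SD of 30 for the within-patient difference, and two-sided 5% tests. The gap between per-stratum and joint power does not depend on the exact SD; its size does. The protocol should state the joint power and tie the test to the strata. The documents do not support going further, either to call the 22 an error or to require that a pooled contrast become the primary test; a pooled test would not serve the all-strata aim.

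**What to change.** **Section 4.4.** State that 80% is a nominal per-stratum figure (about 77% by the paired t-test with 22 evaluable infants), and that power for success in all three strata is about 45-51%. Give the assumptions alongside: difference 18, SD 30 as the SD of the within-patient difference, two-sided 5%, same effect in each stratum.

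**Section 10.1.** State that automated versus manual control is compared within each ventilation stratum. State that the algorithm is concluded to work in all three strata only if all three comparisons are significant at 5%, for which no alpha adjustment is needed. Otherwise, report stratum-specific estimates with 95% confidence intervals and limit the conclusion to what they support.

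**Cost.** Wording in two sections and no extra infants. The downside is that the protocol then shows a less favourable power for the all-strata claim.
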